4.5.3.2.3. Permitted Medications

Apart from the prohibited medications listed in Section 4.5.3.3 treatment with concomitant medications is permitted throughout the study. This includes oral contraceptives, nasal and inhaled corticosteroids, and oral antihistamines. All concomitant medicines must be locally approved and administered at a dose that is considered standard-of-care for the treated indication. It is required that these medications are given at a stable dose prior to study entry and preferably continued without variation of dose or regimen during the study.

In a case where additional concomitant medication need to be administered or dose adjustments for pre-existing conditions (except for AD) need to be performed during the study, the risk/benefit ratio to the subject must be carefully assessed and consideration given to the timing of any necessary introduction of new medications. Continuation of the subject should be reviewed and can be discussed with the medical monitor if needed.

Oral antibiotics to treat atopic dermatitis-associated superficial skin infections are also permitted for up to two weeks duration.

4.5.3.3. Prohibited Concomitant Medications and Procedures

The following medications are prohibited throughout the study participation:

- Systemic corticosteroids
- Topical tacrolimus and pimecrolimus
- Leukotriene inhibitors
- Allergen immunotherapy
- Systemic treatment for AD with an immunosuppressive / immunomodulating substance (including but not limited to, cyclosporine, mycophenolate-mofetil, azathioprine, methotrexate, biologics or interferon gamma or investigational drugs other than MOR106)
- Treatment with a live (attenuated) vaccine
- Photopheresis, immunoapharesis/-adsorption

The following concomitant procedures are prohibited throughout study participation:

- Elective major surgical procedures
- Concomitant ultraviolet (UV) procedures (phototherapy [narrow band UVB, UVB, UVA1 or PUVA1])
- Tanning in a bed/ booth

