4.5. Clinical Study Population

4.5.1. Inclusion Criteria

Subjects must meet all of the following inclusion criteria to be eligible for participation in this study.

- 1. Able and willing to comply with the protocol requirements, and signing the informed consent form (ICF) as approved by the IEC/IRB, prior to any screening evaluations.
- 2. Male or female between 18-65 years of age (extremes included), on the day of signing the ICF.
- 3. A BMI between 18-40 kg/m², inclusive.
- 4. Diagnosis of AD for at least one year since first diagnosis as per the Hanifin and Rajka Criteria.
- 5. EASI ≥ 16 at the screening and ≥ 16 at the baseline visit (Day 1 predose).
- 6. IGA score \geq 3 (on the 0 to 4 IGA scale, in which 3 is moderate and 4 is severe) at the screening and baseline visits.
- 7. Greater than or equal to 10% body surface area (BSA) of AD involvement at the screening and baseline visits.
- 8. Willingness to use a non-medicated, simple bland emollient twice daily for at least 7 days before the baseline visit and throughout the study.
- 9. Subject is a candidate for systemic therapy and has a history of inadequate response to TCS or TCI before screening visit, as per investigator's opinion.
- 10. Subject has at least one AD lesion for which treatment with medium potency TCS is indicated.
- 11. Female subjects must have a negative serum pregnancy test at screening and a negative urine pregnancy test at baseline. The exception are women who are surgically sterile (hysterectomy, bilateral salpingectomy and bilateral oophorectomy), or postmenopausal (i.e. at least 12 consecutive months without menstruation, without an alternative medical cause [including hormone replacement therapy]). A determination of follicle stimulating hormone (FSH) can be performed with FSH >35 mIU/mL confirming postmenopausal status without menstruation for ≥24 months.

12. Female subjects of childbearing potential must use a highly effective method of contraception from 28 days prior to the first dose of IMP, throughout the study, and for

at least 24 weeks after the last dose of IMP.

13. Non-vasectomized male subjects with a female partner of childbearing potential must agree to use a condom, in addition to another highly effective form of contraception used by the female partner, from prior to the first dose, throughout the study, and for at least 24 weeks after the last dose of IMP.

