4.5.3.2. Prior and Concomitant Medications

All medications in relation to the treatment of AD that are not allowed in accordance with the inclusion and exclusion criteria should not be used during the study. All allowed standard treatment should remain on a stable dose until completion of the Day 169 (or ED) visit, if possible.

Prior medications (with the exception of medications used for treatment of AD) used in the 3 months prior to Day 1 will be recorded in the electronic case report form (CRF). Medications used for the treatment of AD received during the last 12 months before Day 1 will be recorded in the CRF. These include any systemic therapy, biologics, or phototherapy ever used for the treatment of AD.

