4.5.3.2.1. Topical Corticosteroids (TCS)

Subjects will not use any TCS for at least 7 days prior to the baseline (Day 1) visit.

From Day 1 onwards, all subjects will apply concomitant open-label, once daily treatment with TCS as follows:

- Medium potency TCS (e.g. Triamcinolone 0.1% cream or Mometasone furoate 0.1% cream or another sponsor approved TCS) to be used as per approved label.
- Other topical medications, such as a lower potency TCS or TCI, may be used to treat AD lesions located on the face, flexural, and genital areas as per approved label.
- Once control has been achieved (lesions have cleared or almost cleared), TCS or TCI application to areas from which lesions have (almost) cleared, will, under the supervision of the investigator, be limited to twice weekly in intervals of 3-4 days until the end of the treatment period (D57).
- During the follow-up period (D57 to D169), topical treatment of residual active AD lesions may continue as needed at the investigator's discretion. This treatment can be stepped up or stepped down as clinically indicated per investigator's discretion.
- During the follow-up period (D57 to D169), in the event of an AD flare, initiation or escalation of TCS therapy will be recorded as rescue therapy in the follow-up period.

 All TCS (and TCI if used) use will be recorded daily by the subject in a diary from screening visit onwards and throughout the study and will be reviewed at each onsite visit by the investigator.

Detailed instructions on TCS management will be described in a separate study reference manual.

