4.5.3.5. Food and Beverage Restrictions

Subjects are not allowed to take alcohol 24 hours before screening and each IMP administration and should abstain from alcohol for 24 hours after dosing. Subjects must limit their alcohol intake during the study to no more than three glasses of wine or beer or equivalent per day.

4.5.4. Treatment Discontinuation (Temporarily and Permanently), Subject Withdrawal and Study Termination

A subject may be withdrawn from the clinical study at any time without the subject's consent if the investigator or sponsor determines that it is not in the best interest of the subject to continue participation. In such case, the reason for withdrawal will be documented in the source documents, and the subject will complete the early discontinuation (ED) visit and /or follow-up visits for safety assessments.

Treatment with IMP should be discontinued by the investigator (preferably after discussion with the CRO medical monitor, who may consult and must inform the sponsor's study physician) for any of the following conditions:

- Life-threatening AE or a SAE that places the subject at immediate risk.
- Serious infections deemed related to study treatment by the investigator, and requiring parenteral antimicrobial therapy and/or hospitalization.

MOR106-CL-204

- Confirmed pregnancy in a female subject or female partner of a male subject (due to likely unblinding of the subject).
- Arrhythmia or conduction abnormality, including but not limited to prolonged QT interval corrected for the heart rate using Fridericia's formula (QTcF), where the severity is categorized as Common Terminology Criteria for Adverse Events (CTCAE) Grade 3 or higher (QTc >500 ms on at least two separate ECGs).
- Increase in liver function tests (LFTs):
 - Aspartate aminotransferase (AST) and/or alanine aminotransferase (ALT) elevations >8x ULN: IMP treatment should be withheld and the LFTs should be repeated. IMP should be discontinued permanently if the results are confirmed.
 - AST and/or ALT elevations >3x ULN and <8x ULN: IMP treatment should be withheld.
 - If LFTs do not return to normal within 2 weeks then the IMP should be discontinued permanently.

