Every effort should be made to keep subjects in the study and on treatment. However, the investigator can consider stopping the treatment with IMP, preferably after consultation with the sponsor's study physician, in case of concerns about the subject's safety, major protocol noncompliance, serious or severe AEs or worsening of the disease condition,

Galapagos MOR106-CL-204

which in the investigator's opinion needs an alternative treatment approach not being covered in the clinical study (e.g. rescue medication).

When study treatment is discontinued, the subject will be requested to return for Early Treatment Discontinuation (ETD) visit and will be asked to continue the follow-up period until end of study.

Subjects will be informed prior to clinical study entry that they are allowed to withdraw from the clinical study. At any time and for any reason, a subject's participation in the clinical study may terminate at his/her request without prejudice to his/her future medical care. The subject will be encouraged to share the reason(s) for withdrawal so this can be documented in the source documents, and to complete the ED/ETD visit and follow-up visits for safety assessments, but will not be obliged to do so.

Subjects who withdraw from the clinical study without contact with the site (lost-to-followup) should be contacted by the site so that their health status can be assessed and documented in the source documents. The site should make every effort to understand whether the subject is alive, including checking the medical records and contacting general practitioner or relatives, if necessary. All attempts must be documented in the source documents.

The sponsor has the right to terminate the clinical study at any time in case of safety concerns or if special circumstances concerning the IMP or the company itself occur, making further treatment of subjects impossible. In this event, the investigator(s) and relevant authorities will be informed of the reason for clinical study termination.

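### The ban on systemic AD therapy and phototherapy has no exception after IMP is stopped, although Section 4.5.4 foresees worsening that needs other treatment and asks that subject to stay in follow-up

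*Protocol*

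**What the plan says.** **The ban.** Protocol 4.5.3.3 introduces its list of medications with "The following medications are prohibited throughout the study participation". The list includes systemic corticosteroids and systemic immunosuppressive or immunomodulating AD treatment, biologics among them. A second list, with the same duration, covers UV phototherapy. Section 4.5.3.2 adds that AD medications not allowed "in accordance with the inclusion and exclusion criteria should not be used during the study". Neither section ends the restriction at the last dose.

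**Stopping IMP.** Section 4.5.4 lets the investigator consider stopping IMP for worsening that "needs an alternative treatment approach not being covered in the clinical study (e.g. rescue medication"). A subject whose treatment is discontinued has an ETD visit and "will be asked to continue the follow-up period until end of study". Section 6.1 places the ETD visit 14 days after the last dose and the last follow-up visit 112 days after ETD.

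**Leaving.** Under Section 4.5.4 a subject may leave at any time "without prejudice to his/her future medical care". If the investigator or sponsor withdraws the subject, "the subject will complete the early discontinuation (ED) visit and /or follow-up visits for safety assessments". A subject who chooses to leave is encouraged, but not obliged, to attend such visits.

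**What stays allowed.** Section 4.5.3.2.1 permits topical step-up in follow-up and says that in a flare "initiation or escalation of TCS therapy will be recorded as rescue therapy in the follow-up period". Section 4.5.3.2.3 allows oral antihistamines, and oral antibiotics for up to two weeks for AD-associated skin infection.

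**Population.** Inclusion criterion 9 reads: "Subject is a candidate for systemic therapy and has a history of inadequate response to TCS or TCI before screening visit", as judged by the investigator.

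**The concern.** The protocol anticipates that a subject may worsen enough to need treatment it does not provide. It wants that subject kept under observation, yet it prohibits the main treatments beyond topicals for the whole of that observation. For a subject who needs one of them, treatment and compliant follow-up cannot be combined.

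Two things are at stake. The first is the patient's position: nobody should have to weigh needed treatment against safety follow-up. The second is data. The primary endpoint (4.3.1) counts TEAEs, SAEs and AESIs to Day 169 or ED, and Section 4.2.2 gives ADA development after treatment stop as one reason for the 16-week follow-up. Subjects who leave for this reason do so because they worsened, so the loss is related to outcome. If they deviate and stay, their safety data are kept, but the protocol neither tells the site to record the therapy as rescue nor confirms that participation continues.

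**Working it through.** **1. Does any provision make a banned class compliant after IMP is stopped?**

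| Provision | What it offers | Resolves it? |
|---|---|---|
| 4.5.3.3 and 4.5.3.2 | Ban for all of participation; no exception at IMP stop | No |
| 4.5.3.2.1 | Topical start or step-up, recorded as rescue | Only if topicals suffice |
| 4.5.3.2.3 | Antihistamines and short antibiotic courses; its rule on new or adjusted medication excludes AD and is subject to the prohibited list | No |
| 4.5.4, withdrawal | Exit with an ED visit and/or safety visits | Compliant, but gives up the follow-up requested |
| SAP 8.1.5 | Excludes efficacy data after rescue | No; the ban is unchanged |

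Section 4.5.4 does not name systemic therapy. The inference that it can mean systemic therapy rests on criterion 9 and on topicals already being covered.

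**2. How long the ban lasts after the last dose.** ETD is last dose + 14 days and follow-up ends at ETD + 112, so 14 + 112 = 126 days.

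| Last dose | ETD | Last visit | Planned days from Day 1 | Share lost if the subject leaves at ETD |
|---|---|---|---|---|
| Day 1 | Day 15 | Day 127 | 126 | 112/126 = 89% |
| Day 15 | Day 29 | Day 141 | 140 | 112/140 = 80% |
| Day 29 | Day 43 | Day 155 | 154 | 112/154 = 73% |

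**3. Samples in follow-up.** The Schedule of Activities has 8 PK samples (Days 71 to 169, every 14 days) and 4 ADA samples (Days 85, 113, 141 and 169) after Day 57/ETD. I assume the visits after an early ETD follow the same pattern. A subject who leaves soon after ETD with one ED visit gives 1 of the 8 and 1 of the 4. The schedule's ED column includes both, although Section 4.5.4 describes visits after withdrawal as being for safety.

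**4. Effect on the protocol's detection figure.** Section 7.1 states 87% for 40 MOR106 subjects and 5% incidence. This reproduces: 1 − 0.95^40 = 0.871. No exit rate is given, so I assume 5% to 15%; the top matches the attrition implied by 51 evaluable of 60 (1 − 51/60 = 15%). Treating leavers as contributing nothing, which overstates the loss because they are observed up to ETD:

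- 2 of 40 leave: 1 − 0.95^38 = 0.858
- 4 of 40 leave: 1 − 0.95^36 = 0.842
- 6 of 40 leave: 1 − 0.95^34 = 0.825

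**5. Observation time lost.** If 3 to 9 of 60 subjects leave at ETD with no later contact, 3 × 112 = 336 to 9 × 112 = 1,008 subject-days are lost. Against 60 × 168 = 10,080 this is 3.3% to 10.0%. The shorter schedule of early stoppers changes this little: with 9 stoppers last dosed on Day 1, planned time is 51 × 168 + 9 × 126 = 9,702 days, and 1,008/9,702 = 10.4%.

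**6. SAP timing categories.** SAP 9.7.2 has three: ended before first dose; started from first dose to last dose + 30 days; started before first dose and continued. A therapy started later fits none, and Table 14.1.3.6 takes only the last two. The uncovered part is 126 − 30 = 96 of the 126 days after the last dose (76%).

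**The case against.** The strongest reply is that the conflict rests on an inference. Section 4.5.4 speaks only of an alternative approach with rescue as the example, and the only rescue the protocol describes is topical. A subject could stop IMP, enter follow-up, step up TCS and stay, fully in compliance. That stands for anyone whom topicals can control. It does not cover the rest, and criterion 9 makes such subjects plausible.

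Several stronger readings are tempting but unsupported:

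- **That every non-topical treatment is banned.** Antihistamines and short antibiotic courses are allowed.
- **That the subject must leave.** No rule says that taking a prohibited drug ends participation. SAP 8.1.5 and Listing 16.2.4.8 expect some subjects to take rescue and remain. SAP 8.1.7 keeps safety data to the last follow-up visit. With no per-protocol set (SAP 8.2.1), a deviation does not remove anyone from the AE or ADA analysis, although the PK set may exclude deviations.
- **That the SAP cannot show such therapy.** Listing 16.2.4.6 shows all therapy records with linked AEs, Listing 16.2.10.2 names medication started because of an AE, and Listing 16.2.10.14 covers non-drug therapies. Worsening of AD can itself be an AE (Protocol 9.1.1). Listing 16.2.4.7 does not help, as it selects only TCS/TCI.
- **That completers face the same conflict.** They face the same ban, but the request in 4.5.4 concerns subjects whose treatment was discontinued.

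A continuing ban also has a rationale: it keeps late AE and ADA data interpretable. This supports a narrow exception rather than none.

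**Conclusion.** The point holds in a limited form. For a subject who stops IMP because of worsening and needs systemic therapy or phototherapy, the protocol leaves withdrawal or deviation, over a follow-up of 112 days after ETD. It matters mainly for the patient's position and for keeping outcome-related exits out of the primary-endpoint follow-up.

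The number affected is unknown and probably small. Under the assumed 5% to 15% exit rates, detection of a 5% event falls from 87% to between 86% and 83% at worst, and 3% to 10% of observation time is lost. A reader might infer that the safety evaluation is materially weakened. The documents do not support that: safety analysis is descriptive (SAP 14), safety visits after withdrawal are possible, and Section 9.3.2 provides for later SAEs relevant to IMP to be reported. The change is worth making because it is cheap.

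The SAP category gap is real but secondary, and it affects any late-started therapy. A country-specific protocol for Latvia and Georgia, listed in SAP 1.1, is not among the documents, so its handling of this point is unknown.

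**What to change.** **Protocol.** In 4.5.4, with matching exceptions in 4.5.3.2 and 4.5.3.3, state that after permanent IMP discontinuation:

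- medically necessary systemic AD therapy or phototherapy may be started for worsening;
- it is recorded as rescue;
- it does not end participation;
- AE, AESI, PK and ADA collection continues to ETD + 112 days.

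The ban otherwise stays. Extending the exception to completers in follow-up is optional.

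**SAP, secondary.** In 9.7.2 add a category for therapies started more than 30 days after the last dose, and tabulate them beside Table 14.1.3.6. A dedicated flag for AEs, ADA and PK samples after the start of rescue is optional, given the listings.

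**Cost.** One protocol statement, two matching exceptions and one SAP category. Sample size and endpoints do not change. The downside is that some late AE and ADA data will be confounded by the new therapy. Limiting the exception to medically necessary treatment after permanent IMP stop keeps this small, and Listings 16.2.4.6, 16.2.4.8, 16.2.10.2 and 16.2.10.14 make it visible without removing it.

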4.5.3.4. Rescreening

Subjects may only be rescreened with the approval of the medical monitor. If a subject is rescreened, all screening assessments will be repeated and a new screening number will be applied. If a subject is rescreened, the screening window will begin once the first rescreening assessment has been initiated.

4.5.3.5. Food and Beverage Restrictions

Subjects are not allowed to take alcohol 24 hours before screening and each IMP administration and should abstain from alcohol for 24 hours after dosing. Subjects must limit their alcohol intake during the study to no more than three glasses of wine or beer or equivalent per day.

4.5.4. Treatment Discontinuation (Temporarily and Permanently), Subject Withdrawal and Study Termination

A subject may be withdrawn from the clinical study at any time without the subject's consent if the investigator or sponsor determines that it is not in the best interest of the subject to continue participation. In such case, the reason for withdrawal will be documented in the source documents, and the subject will complete the early discontinuation (ED) visit and /or follow-up visits for safety assessments.

Treatment with IMP should be discontinued by the investigator (preferably after discussion with the CRO medical monitor, who may consult and must inform the sponsor's study physician) for any of the following conditions:

- Life-threatening AE or a SAE that places the subject at immediate risk.
- Serious infections deemed related to study treatment by the investigator, and requiring parenteral antimicrobial therapy and/or hospitalization.

MOR106-CL-204

- Confirmed pregnancy in a female subject or female partner of a male subject (due to likely unblinding of the subject).
- Arrhythmia or conduction abnormality, including but not limited to prolonged QT interval corrected for the heart rate using Fridericia's formula (QTcF), where the severity is categorized as Common Terminology Criteria for Adverse Events (CTCAE) Grade 3 or higher (QTc >500 ms on at least two separate ECGs).
- Increase in liver function tests (LFTs):
 - Aspartate aminotransferase (AST) and/or alanine aminotransferase (ALT) elevations >8x ULN: IMP treatment should be withheld and the LFTs should be repeated. IMP should be discontinued permanently if the results are confirmed.
 - AST and/or ALT elevations >3x ULN and <8x ULN: IMP treatment should be withheld.
 - If LFTs do not return to normal within 2 weeks then the IMP should be discontinued permanently.
 - If LFTs return to normal within 2 weeks then IMP could be restarted with close monitoring (e.g. repeat testing twice per week for the first 2 weeks then weekly for the following month). In the event LFTs become abnormal at any subsequent point during the trial (i.e. after rechallenge) then the IMP should be permanently discontinued.
 - AST and/or ALT elevations >3x ULN **and** total bilirubin level (TBL) >2x ULN or international normalized ratio (INR) >1.5: IMP treatment should be withheld and the LFTs should be repeated. IMP should be discontinued permanently if the results were confirmed.
 - AST and/or ALT elevations >3x ULN with the appearance of fatigue, nausea, vomiting, right upper quadrant pain or tenderness, fever, rash and/or eosinophilia (>5%): IMP treatment should be withheld, LFT repeated and IMP discontinued if LFT confirmed **or** if symptoms and signs persist.

When test results need to be confirmed, the subject should return to the investigational site and be evaluated as soon as possible, preferably within 48 hours from awareness of the abnormal results. This evaluation should include laboratory tests, detailed history and physical assessment. In addition to repeating AST and ALT, laboratory tests should include albumin, creatine kinase, total bilirubin, direct and indirect bilirubin, gamma glutamyl transferase (GGT), INR, and alkaline phosphatase. A detailed history, including relevant information (e.g. review of ethanol, recreational drug and supplement consumption, family history, sexual history, travel history, history of contact with a jaundiced subject, surgery, blood transfusion, history of liver or allergic disease, and work exposure) should be collected. Further testing for acute hepatitis A, B or C infection and liver imaging (e.g. biliary tract) may be warranted. All cases confirmed on repeat testing with no other cause for LFT abnormalities identified at the time should be considered potential Hy's Law cases irrespective of availability of all the results of the investigations performed to determine etiology of the abnormal LFTs. Such potential Hy's Law cases should be reported as SAEs.

Every effort should be made to keep subjects in the study and on treatment. However, the investigator can consider stopping the treatment with IMP, preferably after consultation with the sponsor's study physician, in case of concerns about the subject's safety, major protocol noncompliance, serious or severe AEs or worsening of the disease condition,

Galapagos MOR106-CL-204

which in the investigator's opinion needs an alternative treatment approach not being covered in the clinical study (e.g. rescue medication).

When study treatment is discontinued, the subject will be requested to return for Early Treatment Discontinuation (ETD) visit and will be asked to continue the follow-up period until end of study.

Subjects will be informed prior to clinical study entry that they are allowed to withdraw from the clinical study. At any time and for any reason, a subject's participation in the clinical study may terminate at his/her request without prejudice to his/her future medical care. The subject will be encouraged to share the reason(s) for withdrawal so this can be documented in the source documents, and to complete the ED/ETD visit and follow-up visits for safety assessments, but will not be obliged to do so.

Subjects who withdraw from the clinical study without contact with the site (lost-to-followup) should be contacted by the site so that their health status can be assessed and documented in the source documents. The site should make every effort to understand whether the subject is alive, including checking the medical records and contacting general practitioner or relatives, if necessary. All attempts must be documented in the source documents.

The sponsor has the right to terminate the clinical study at any time in case of safety concerns or if special circumstances concerning the IMP or the company itself occur, making further treatment of subjects impossible. In this event, the investigator(s) and relevant authorities will be informed of the reason for clinical study termination.

